**HOG Protocol: BRE09-146**

TITLE	PARP Inhibition after Preoperative Chemotherapy in Patients with Triple Negative Breast Cancer or ER/PR +, HER2 negative with known BRCA1/2 Mutations: Hoosier Oncology Group															
STUDY PHASE	II															
OBJECTIVES	
Primary Objective:
 
 
• To evaluate 2-year disease-free survival (DFS), in patients with confirmed TNBC or ER/PR + HER2-, known BRCA1/2 mutations treated with single agent cisplatin and patients treated with cisplatin in combination with rucaparib following preoperative chemotherapy
 
 
Secondary Objectives:
 
 
• To characterize the side effects and tolerability of cisplatin and cisplatin plus rucaparib in patients with residual disease following preoperative chemotherapy.
 
• To evaluate 1-year DFS
 
• To determine 5-year overall survival
 
• To collect limited pharmacokinetic data, in patients receiving study drug to compliment ongoing PK analyses in other trials with rucaparib
 
• To collect archived tumor specimens, and genomic DNA to explore potential correlates of PARP inhibition, recurrence and toxicity. To compare limited PK parameters between the IV and oral formulation of rucaparib
 
															
STUDY DESIGN	
Safety Run-in Cohorts
 
Drug interaction and increased toxicity is not anticipated, however there is no clinical experience with cisplatin + rucaparib. To exclude prohibitive toxicity, 6 patients will be treated with combined therapy as outlined in Table 1.
 
Table 1: Treatment plan for Safety Run-in Cohorts
 
  
 Drug	Dose	Frequency of administration	Route of administration	Number of cycles	
   
 Rucaparib (administered as the phosphate salt)	 Cohort 1:            16 mg C1*            24 mg C2-4    Cohort 2:            24 mg C1*            30 mg C2-4         	D1,2,3 every 21 days	IV ** followed in one hour by Cisplatin	4	
 
 Cisplatin	75 mg/m^2	D1 every 21 days	IV infusion per institutional guidelines	4	
  
 
*NOTE: rucaparib dose should be increased to 24 mg for cohort 1 or 30 mg for cohort 2 during cycles 2-4 in the absence of dose limiting toxicity (as defined in Table 2) in cycle 1.
 
**NOTE:
 
 
• 16 mg dose: ~32 minute infusion time, ~117 mL infusion volume
 
• 24 mg dose: ~33 minute infusion time, ~120 mL infusion volume
 
• 30 mg dose: ~34 minute infusion time, ~124 mL infusion volume
 
	Drug	Dose	Frequency of administration	Route of administration	Number of cycles	Rucaparib (administered as the phosphate salt)	Cohort 1: 16 mg C1* 24 mg C2-4  Cohort 2: 24 mg C1* 30 mg C2-4	D1,2,3 every 21 days	IV ** followed in one hour by Cisplatin	4	Cisplatin	75 mg/m 	D1 every 21 days	IV infusion per institutional guidelines	4
Drug	Dose	Frequency of administration	Route of administration	Number of cycles												
Rucaparib (administered as the phosphate salt)	Cohort 1: 16 mg C1* 24 mg C2-4  Cohort 2: 24 mg C1* 30 mg C2-4	D1,2,3 every 21 days	IV ** followed in one hour by Cisplatin	4												
Cisplatin	75 mg/m 	D1 every 21 days	IV infusion per institutional guidelines	4												

Volume calculated using an assumed standard overfill of 9 mL in a 100 mL commercial bag of D5W plus the required volume of reconstituted drug product for a specific dose.

**Randomization Portion of Study:**

During the randomized portion of the study, patients will be randomized to either Arm A or Arm B.

**Arm A (cisplatin monotherapy)**

**Table 3: Treatment Plan – Arm A**

Drug	Dose	Frequency of administration	Route of administration	Number of cycles
Cisplatin	75 mg/m 	D1 every 21 days	IV infusion per institutional guidelines	4

**Arm B (combination therapy)**

**Table 4: Treatment plan - Arm B**

Drug	Dose	Frequency of administration	Route of administration	Number of cycles
Rucaparib	24 mg C1* 30 mg C2-4	D1,2,3 every 21 days	IV ** followed in one hour by Cisplatin	4
Cisplatin	75 mg/m 	D1 every 21 days	IV infusion per institutional guidelines	4

**\*NOTE:** Rucaparib dose should be increased to 30 mg for cycles 2-4 in the absence of dose limiting toxicity (as defined in Table 2) in cycle 1

**\*\*NOTE: 24 mg dose:** ~33 minute infusion time, ~120 mL infusion volume\*

**30 mg dose:** ~34 minute infusion time, ~124 mL infusion volume\*

\*Volume calculated using an assumed standard overfill of 9 mL in a 100 mL commercial bag of D5W plus the required volume of reconstituted drug product for a specific dose.

**Rucaparib maintenance therapy for Safety Run-in and Arm B**

**Table 5: Treatment plan – IV Maintenance therapy**

**NOTE:** All patients should proceed with oral rucaparib maintenance therapy after approval of Amendment #5 and when oral drug available.

Drug	Dose	Frequency of administration	Route of administration	Number of weeks
Rucaparib	30 mg	Weekly	IV **	24

**\*\*NOTE:**

**30 mg dose:** ~34 minute infusion time, ~124 mL infusion volume

Volume calculated using an assumed standard overfill of 9 mL in a 100 mL commercial bag of D5W plus the required volume of reconstituted drug product for a specific dose.

**Table 6: Treatment plan – Oral maintenance therapy**

Drug	Dose	Frequency of administration	Route of administration	Number of weeks
Rucaparib (administered as the camsylate salt)	100 mg total (1-60 mg tab + 1-40 mg tab)	Weekly	Oral	24

NUMBER OF PATIENTS	Total number of patients = 135
ELIGIBILITY	
 
Written informed consent and HIPAA authorization for release of personal health information. NOTE: HIPAA authorization may be included in the informed consent or obtained separately.
 
Age <math>\geq</math> 18 years at the time of consent.
 
ECOG Performance Status 0 or 1 within 30 days prior to registration for protocol therapy.
 
Women of childbearing potential and males must be willing to use an effective method of contraception from the time consent is signed until 4 weeks after treatment discontinuation.
 
Women of childbearing potential must have a negative pregnancy test within 14 days prior to registration for protocol therapy. NOTE: Women are considered not of child bearing potential if they are surgically sterile (they have undergone a hysterectomy, bilateral tubal ligation, or bilateral oophorectomy) or they are postmenopausal.
 
Women must not be breastfeeding.
 
Must have histologically or cytologically confirmed triple negative (ER-/PR-/HER2-) invasive breast cancer, stage I-III at diagnosis (AJCC 6th edition) based on initial evaluation by clinical examination and/or breast imaging. NOTE: ER- and PR- should meet one of the following criteria: 
 
Local Pathology report classifies them as negative
 
Allred Score of 2 or below
 
<5% weakly positive staining
 
 
 
 
Patients with ER+ and/or PR+ may enroll ONLY if they are known carriers of a deleterious mutation in BRCA1 or BRCA2. Patients with HER2+ tumors may not enroll regardless of BRCA status.
 
 
Must have completed preoperative (neoadjuvant) chemotherapy. NOTE: Acceptable preoperative regimens include an anthracycline or a taxane, or both. Patients may NOT have received cisplatin as part of their neoadjuvant therapy regimen. Patients who received preoperative therapy as part of a clinical trial may enroll. No adjuvant chemotherapy after surgery other than that specified in this protocol is allowed. Adjuvant bisphosphonate use is allowed.
 
Must have completed definitive resection of primary tumor. The last surgery for breast
 


cancer must have been completed at least 14 days prior to registration for protocol therapy.

**NOTE:** Negative margins for both invasive and ductal carcinoma *in situ* (DCIS) are desirable, however patients with positive margins may enroll if the treatment team believes no further surgery is possible and patient has received radiotherapy. Patients with margins positive for lobular carcinoma *in situ* (LCIS) are eligible. Either mastectomy or breast conserving surgery (including lumpectomy or partial mastectomy) is acceptable. Sentinel node biopsy is allowed but axillary dissection is strongly encouraged in patients with lymph node involvement.

- Must have significant residual invasive disease at the time of definitive surgery following preoperative chemotherapy. Significant residual disease is defined *at least one of the following*:
  - Miller-Payne response in the breast of 0-2. (Please refer to Study Procedure Manual[SPM])
  - Residual Cancer Burden (RBC) classification II or III
  - Residual carcinoma in one or more regional lymph nodes that would meet AJCC 6th edition criteria for N1 - N3 disease.
  - Alternatively, if Miller-Payne or RCB grading is not available, the patient will be eligible if the pathology report indicates that the area of residual invasive disease in the breast measures at least 2 cm following preoperative therapy. The presence of DCIS without invasion does not qualify as residual disease in the breast.
- Whole breast radiotherapy is required for patients who underwent breast conserving therapy, including lumpectomy or partial mastectomy. Patients receiving adjuvant radiation therapy must have completed radiotherapy at least 14 days prior to registration for protocol therapy.

**NOTE:** Post-mastectomy radiotherapy is required for all patients with a primary tumor  $\geq 5$  cm or involvement of 4 or more lymph nodes. For patients with primary tumors  $< 5$  cm or with  $< 4$  involved lymph nodes, provision of post-mastectomy radiotherapy is at the discretion of the treating physician.

- Patients must enroll within 84 days of surgery (for those patients who do not require radiation) or within 84 days of completion of radiation when radiation is required
- No stage IV (metastatic) disease, however no specific staging studies are required in the absence of symptoms or physical exam findings that would suggest distant disease.
- No treatment with any investigational agent within 30 days prior to registration for protocol therapy.
- No history of chronic hepatitis B or C

**Laboratory values must be obtained within 14 days prior to registration for protocol therapy.**

- Hemoglobin (Hgb)  $\geq 9.0$  g/dL
- Platelets  $\geq 100$  K/ mm^3
- Absolute neutrophil count (ANC)  $\geq 1.5$  K/mm^3
- Calculated creatinine clearance of  $\geq 50$  cc/min using the Cockcroft-Gault formula:
  - Males:  $(140 - \text{Age in years}) \times \text{Actual Body Weight in kg}$
  - $72 \times \text{Serum Creatinine (mg/dL)}$
- Females: Estimated creatinine clearance for males  $\times 0.85$
- Bilirubin  $\leq$  upper limit of normal (except in patients with documented Gilbert's disease,

	
who must have a total bilirubin <math>\leq</math> 3.0 mg/dL)
 
 
• Aspartate aminotransferase (AST, SGOT) <math>\leq 2.5 \times</math> ULN
 
• Alanine aminotransferase (ALT, SGPT) <math>\leq 2.5 \times</math> ULN
 
• Left ventricular ejection fraction within normal limits obtained within 30 days prior to registration for protocol therapy.
 
 
NOTE: Patients with an unstable angina or myocardial infarction within 12 months of study entry are excluded.
 
 
• No clinically significant infections as judged by the treating investigator.
 
• Must consent to allow submission of archived tumor tissue sample from definitive surgery.
 
• Must consent to collection of blood samples for PK analysis.
 
• No clinically significant arrhythmia or baseline ECG abnormalities in the opinion of the treating investigator.
 

STATISTICAL CONSIDERATIONS	
Sample Size Justification The primary endpoint for this trial is 2 year DFS. In order to detect an improvement of the fraction of patients free from disease at 2-year from 40% in the control arm to 63.2% in the rucaparib arm (corresponding to an HR=0.5), 38 events are needed to have 80% power to detect a difference in DFS using a one-side log-rank test with 0.10 level of significance (calculation done using nQuery Advisor 7.0 and assuming exponential survival). In order to observe 38 events we need to accrue about 102 patients, with an accrual time of about 13-18 months and an overall study duration around 25-30 months. In addition, 6 patients will be needed at the lower dose (cohort 1). Assuming ~20% will not be confirmed to have TNBC on central review; the total sample size will be increased to 128 to ensure 102 in the primary analysis (using cohort 2 and the randomized patients) and 6 in the safety analysis for cohort 1.
 
Patient Characteristics Patient characteristics will be summarized by treatment group for demographics, baseline disease characteristics, and medical history. The two treatment groups will be compared using standard methods such as t-tests and chi-square tests.
 
Interim Safety Analyses The first 12 patients (6 in cohort 1 and 6 in cohort 2) will be assigned to the PF-01367338 arm for an initial safety run-in. A safety analysis will be done after all six patients in each cohort have completed cycle 2. All toxicities will be tabulated. The study will move forward to cohort 2 if <math>\leq 1</math> of 6 in cohort 1 experience a DLT (as defined in Section 5.1). If <math>\geq 2</math> of 6 in cohort 1 experience a DLT, the study will be suspended and an amendment to explore alternate dosing schemes will be considered. Similarly, if <math>\leq 1</math> of 6 in cohort 2 experience a DLT (as defined in Section 5.1), the randomized portion will commence. If <math>\geq 2</math> of 6 in cohort 2 experience a DLT, the study will be suspended and an amendment to proceed with the randomized portion with the cohort 1 dose will be considered. Once the decision is made to move forward with the randomized portion a second safety analysis will be conducted after the first 40 patients (~20 from each group) have been randomized and completed 2 cycles of treatment. Toxicity counts and rates will be tabulated by treatment arm in a blinded fashion. The study will be terminated if the probability that the DLT rate equals 20% or less in either arm drops below .10. Accrual will continue during the interim analysis. The results of the analysis will be submitted to the CTMC for external review.
 
Analysis of Primary Objective The comparison of DFS between the two groups will be made using an unstratified Kaplan-Meier analysis with a log-rank test to test for differences using the patients in safety run-in cohort 2 and the randomized portion of the study. A specific comparison of 2-year DFS will be


made using a two-sample test based on the complementary log-log transformation as suggested in Klein, et al. As supportive analysis, a stratified log-rank test will be done using the stratified randomization factors neoadjuvant anthracycline versus not and lymph node involvement at time of definitive surgery versus not. In addition, sensitivity analyses using Cox regression may be carried out to identify prognostic factors and provide adjusted estimates of the treatment group differences in DFS.

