### **12.1 Sample Size Justification**

The primary endpoint for this trial is 2 year DFS. In order to detect an improvement of the fraction of patients free from disease at 2-year from 40% in the control arm to 63.2% in the rucaparib arm (corresponding to an HR=0.5), 38 events are needed to have 80% power to detect a difference in DFS using a one-side log-rank test with 0.10 level of significance (calculation done using nQuery Advisor 7.0 and assuming exponential survival). In order to observe 38 events we need to accrue about 102 patients, with an accrual time of about 13-18 months and an overall study duration around 25-30 months. In addition, 6 patients will be needed at the lower dose (cohort 1). Assuming ~20% will not be confirmed to have TNBC on central review; the total sample size will be increased to 135 to ensure 102 in the primary analysis (using cohort 2 and the randomized patients) and 6 in the safety analysis for cohort 1.

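### The synopsis statistics text gives a total of 128 where the rest of the protocol gives 135; at the plan's own 20% loss, 128 yields about 98 primary-analysis patients, not 102

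*Combined protocol and SAP*

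**What the plan says.** The total sample size appears in three places in the current protocol.

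- Synopsis, Statistical Considerations, Sample Size Justification: "the total sample size will be increased to 128 to ensure 102 in the primary analysis".
- Section 12.1, Sample Size Justification: "the total sample size will be increased to 135 to ensure 102 in the primary analysis".
- Synopsis, Number of Patients row: "Total number of patients = 135".

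The first two are the same sentence in the same paragraph, and the inputs around them are identical. The design uses 2-year DFS of 40% against 63.2% (hazard ratio 0.5), "using a one-side log-rank test with 0.10 level of significance", and states that "38 events are needed to have 80% power to detect a difference in DFS". It then says "In order to observe 38 events we need to accrue about 102 patients". Accrual is put at 13–18 months and the whole study at 25–30 months. Six further patients are needed for cohort 1 at the lower dose, and about 20% are assumed not to be confirmed as TNBC on central review. Both versions say that the 102 come from cohort 2 and the randomized patients, with the 6 in cohort 1 counted for safety. Section 12.4 uses the same population for the primary comparison.

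**The concern.** Two totals, 7 patients apart, are attached to one set of assumptions, so at most one of them can be the intended result. The synopsis also disagrees with itself, because its own patient-number row gives 135. The total sample size is the accrual target, and the protocol has no rule for which figure governs. The lower figure also appears not to do what its sentence claims: it is meant to cover 102 primary-analysis patients after the central-review loss and 6 cohort 1 patients as well. What is at stake is the consistency of a figure that the trial relies on and, to a lesser degree, the size of the primary-analysis set behind the 38-event calculation.

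**Working it through.** **Inputs.** From the synopsis Sample Size Justification and Section 12.1: hazard ratio 0.5, one-sided alpha 0.10, power 80%, 38 events, 102 primary-analysis patients, 6 cohort 1 patients outside that set, about 20% not confirmed, accrual 13–18 months, total duration 25–30 months. Assumptions: 1:1 allocation (no ratio is stated; Section 12.3 expects about 20 per group among the first 40 randomized) and uniform accrual. Exponential survival is the plan's own assumption.

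**Step 1: the plan's event count.** Schoenfeld: events = 4 × (z for 0.90 + z for 0.80)² / (ln 0.5)² = 4 × (1.2816 + 0.8416)² / 0.4805 = 37.5, rounded up to 38. The stated 38 is reproduced, and 38 events give 80.4% power. The event count is not in question.

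**Step 2: the total.** To retain n after losing a fraction d, enrol n/(1 − d).

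- Primary-analysis patients alone: 102/0.8 = 127.5, so 128.
- Adding cohort 1 without inflating it: 128 + 6 = 134.
- Inflating all 108: 108/0.8 = 135.

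As a total that includes cohort 1, 128 is not reproduced. 135 is reproduced exactly if cohort 1 is inflated too, and is 1 above 134 if it is not.

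**Step 3: what each total yields.** Remove the 6 cohort 1 patients, then apply the confirmation rate.

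- 128: (128 − 6) × 0.8 = 122 × 0.8 = 97.6, which is 4.4 below 102.
- 134: (134 − 6) × 0.8 = 102.4.
- 135: (135 − 6) × 0.8 = 129 × 0.8 = 103.2.

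**Step 4: sensitivity to the approximate 20%.** With 122 patients the expected number confirmed is 103.7 at 15% loss, 100.0 at 18%, 97.6 at 20% and 91.5 at 25%. The break-even loss is 1 − 102/122 = 16.4%; for 135 it is 1 − 102/129 = 20.9%. If each patient independently has a 20% chance of not being confirmed, the chance of at least 102 is about 19% from 122 patients and about 65% from 129.

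**Step 5: effect on events and power.** The control hazard is −ln(0.40)/24 = 0.0382 per month, and the rucaparib hazard is half of that. With accrual A and total duration T, the event probability in an arm with hazard λ is 1 − [exp(−λ(T − A)) − exp(−λT)]/(λA). Expected events are n/2 times the sum over the two arms, and power is from Schoenfeld's formula.

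| Accrual / total (months) | n = 102: events, power | n = 97.6: events, power |
|---|---|---|
| 13 / 25 | 40.7, 82% | 38.9, 81% |
| 18 / 30 | 44.3, 85% | 42.4, 84% |
| 18 / 25 | 36.0, 79% | 34.4, 77% |

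The loss is about 1 point in each row. The 18/25 row falls below 38 events even with the full 102. Under the same model, 38 events are expected at 24.4 months with 97.6 patients and 23.4 with 102 when accrual takes 13 months, and at 27.1 against 26.1 months when it takes 18. The delay is about one month and stays within 30 months.

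**The case against.** The strongest reply is that 128 is a figure left over in one sentence and harms nothing. Section 12.1 and the patient-number row agree on 135, so closing accrual at 128 is unlikely, and if it happened, power would fall by about 1 point and the 38th event would come about a month later. That stands, and it limits the weight of the point. It does not remove the contradiction in the accrual target.

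A reader might infer that 128 cannot give 102. The documents do not support that: the 20% is approximate, and a loss of 16.4% or less would be enough. Section 8.0 also admits known BRCA1/2 carriers to the primary endpoint population, so not every patient unconfirmed as TNBC need be lost; the share of carriers is not given. Nor does 135 make 102 certain, at about 65% on the binomial calculation.

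A reader might also conclude that 128 came from forgetting cohort 1, since 102/0.8 rounds up to it. No derivation is shown, and 102 × 1.2 + 6 = 128.4 fits as well while including cohort 1. In the same way, (102 + 6)/0.8 = 135 fits exactly but is not written in the protocol. It inflates a cohort that counts only for safety, and Table 13 takes everyone dosed into the safety set whatever central review finds.

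Finally, footnote B of the Schema puts the run-in patients into the efficacy analysis without naming a cohort. If cohort 1 counted, 128 × 0.8 = 102.4 would be enough. That reading conflicts with the sample-size sentence itself and with Section 12.4, both of which use cohort 2 only, and it would still leave 128 against 135.

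**Conclusion.** The point holds as an inconsistency in current text with a small numerical consequence. The synopsis statistics paragraph is out of step with Section 12.1 and with the synopsis's own patient count. On its stated inputs, 128 falls about 4 patients short of 102 in expectation, whereas 135 meets the target. The shortfall rests on the 20% loss and on keeping cohort 1 out of the primary analysis. The power figures rest on exponential DFS, uniform accrual and 1:1 allocation.

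It would be wrong to read this as an underpowered design. The 38-event calculation is sound, both natural pairings of accrual and duration still exceed 38 expected events with 97.6 patients, and the 77% at 18/25 months should be read against 79% with the full 102. The correction should be made because the total is a figure the trial relies on, not because the primary comparison is at risk.

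**What to change.** In the synopsis Sample Size Justification, replace 128 with 135, so that it agrees with Section 12.1 and the patient-number row. Ask the sponsor to state the derivation of the total once: 102/0.8 + 6 = 134 after rounding up if cohort 1 is not inflated for central-review loss, or 108/0.8 = 135 if it is. The cost is one number and one line of text. No patients are added beyond the 135 already given, and no analysis changes.

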#### **Analysis of Secondary Objectives**

As support for the primary objective, overall DFS and 2-year DFS will be compared using the same techniques above using only the subjects in the randomized part of the study. One-year DFS will be tested using the test described above for 2-year DFS. Safety and tolerability variables will be tabulated separately for the two groups. Incidences of selected adverse events from the two treatment arms may be compared using Fisher's Exact tests on an exploratory basis. OS will be compared between treatment groups using the same methodology as DFS. PK levels will be described using summary statistics. In addition characteristics of tumor specimens and genomic DNA will be correlated with PARP inhibition, recurrence and toxicity. Continuous measures will be correlated with binary variables (e.g. recurrence and toxicity) using maximal chi-square tests and continuous variables (e.g. PARP inhibition) using Pearson or Spearman correlations. Binary variables such as tumor and genomic characteristics will be correlated recurrence and toxicity using chi-square or Fisher's Exact test. All of the analyses with the PK and correlative data are exploratory and are designed to complement efforts in other trials with this agent.

[figure not shown]
**PARP Inhibition after Preoperative Chemotherapy in Patients with Triple Negative Breast  
Cancer (TNBC) or ER/PR + and HER2 negative with known BRCA1/2 Mutations:  
Hoosier Oncology Group BRE09-146**

